2.7 ANALYSIS OF PHARMACOKINETIC DATA

All the pharmacokinetic analyses will be performed using the pharmacokinetic population. Pharmacokinetic sampling will occur with the first infusion at 0.3, 1.0 and 3.0 mg/kg olipudase alfa and at Week 52. Specific time points are detailed in protocol Section 1.5 for each age cohort. To minimize the amount of blood drawn, post-dose time points have been selected for sparse sampling of pharmacokinetic parameters and microsampling methods (volumes \leq 0.5 mL) will be used. If a patient receives only a partial infusion (eg, due to a safety concern), pharmacokinetic sampling will be repeated the next time the patient receives that dose.

2.7.1 Pharmacokinetic parameters

Plasma concentration-time data will be analyzed by noncompartmental methods, or nonlinear mixed effects modeling, based upon patient age and data suitability. Pharmacokinetic parameters if calculated using noncompartmental methods from plasma olipudase alfa concentrations may include, but are not limited to, C_{eio} , C_{max} , t_{max} , AUC_{last} , AUC_{0-t} , $t_{1/2z}$, CL and V_{ss} . Pharmacokinetic parameters if derived from population PK model may include C_{max} , t_{max} , AUC_{0-t} , CL and V .

2.7.2 Statistical analysis

Plasma concentration-time data will be analyzed by non-compartmental methods, or nonlinear mixed effects modeling, based upon patient age and data suitability. Values will be reported for individual patient and summarized by age group cohorts, dose level, [REDACTED] and study week as appropriate.

For ease of presentation, mean values will be arithmetic mean unless specified. Concentration values below the plasma assay limit will be treated as zero in calculating mean values. Mean values below Lower Limit of Quantification (LLOQ) will be reported as LLOQ in the tables and not plotted in the figures if after C_{max} . Mean calculations and their associated statistics will be generated from unrounded numbers and may differ slightly from those values that would be determined using the rounded numbers displayed in the tables. Values expressed in all tables will be for ease of presentation and will not be meant to imply accuracy to more than 3 significant figures.

Pharmacokinetic parameters of olipudase alfa may be summarized using descriptive statistics such as arithmetic mean, geometric mean, SD, standard error of the mean (SEM), coefficient of variation (CV [%]), minimum, median, maximum, and number of observations for each study

visit, dose level and age group cohort under the responsibility of Pharmacokinetics, Dynamics and Metabolism (PKDM) using Phoenix WinNonlin Professional, Version 5.2 or above.

Associations between IgG ADA variables and PK of olipudase alfa may be explored. If applicable, plot of olipudase alfa PK (e.g., AUC) versus PK visit may be provided by ADA classifications.

2.8 ANALYSIS OF EXPLORATORY EFFICACY VARIABLES

All exploratory efficacy analyses to assess changes in organomegaly (spleen and liver), infiltrative lung disease, linear patient growth, pulmonary function, bone age, cycle ergometry endpoints, physician's global assessment, efficacy biomarkers, lipid profile, bone biomarkers, health outcome questionnaires, cognitive functioning and adaptive functioning will be performed using the mITT population. For each exploratory efficacy assessment, observed measures and changes from baseline, as appropriate, will be listed and summarized, including the p-value from analysis of covariance with baseline as covariate and 95% CIs as appropriate, separately by time point, age group cohorts and overall.

Baseline for exploratory efficacy variables will be defined as the last non-missing value before the first infusion.

2.8.1 Spleen and liver volumes

Spleen and liver volumes will be measured by abdominal magnetic resonance imaging (MRI) to quantitate the degree of splenomegaly and hepatomegaly at Screening, Week 26 and Week 52 (or at withdrawal if withdrawn prematurely and not done within 12 weeks prior to withdrawal). MRIs will be collected and read centrally by a third party blinded to patient number and study visit.

Spleen volume ≥ 5 multiples of normal (MN) is an inclusion criterion. For screening purpose, the external vendor will provide the spleen volume in the unit of MN to the site. The computation will use the same formula as below. However, the report from the external vendor will be part of the source document of the site and will not be included in the clinical data base. Spleen and liver volumes collected in cm^3 unit (including those from the screening visit) will be converted to multiples of normal (MN) unit for analyses using the following formula:

$$\text{Spleen Volume (MN)} = \text{Spleen Volume} (\text{cm}^3) / [2 * \text{Weight (kg)}].$$

$$\text{Liver Volume (MN)} = \text{Liver Volume} (\text{cm}^3) / [25 * \text{Weight (kg)}].$$

Change from baseline and percent change from baseline for both cm^3 and MN units, in addition to observed values, will be calculated and summarized for all scheduled visits by age group cohorts and overall. The analysis of covariance (ANCOVA) with baseline as the covariate and Wilcoxon-Mann-Whitney (WMW) test p-values for the change from baseline and percent change from baseline will be provided in the summary tables for spleen/liver volumes in MN unit. Box plots of observed values over time for spleen and liver volumes in MN unit will be provided.

Summary plots for the mean spleen/liver volumes (MN) over time will be provided. By-patient plots of the observed spleen/liver volumes (MN) over time will be provided.

Additional sensitivity analyses to assess the effect of age group cohorts: Analysis of covariance (ANCOVA) will be used for the mITT population for spleen/liver volumes in MN unit with the following model:

Percent change from baseline at Week 26 or 52 volume (MN) = Age group cohorts + Baseline value

The observed values, change from baseline and percent change from baseline on spleen volume (MN) will also be summarized by the following disease severity:

- Spleen volume by baseline spleen volume severity (severe vs not severe). Severity is defined as baseline spleen volume > 15 MN.

In addition, the summary of spleen/liver volumes (MN) over time will be provided to exclude patients who satisfy the noncompliance condition in [Section 2.1.2](#) as a sensitivity analysis if applicable.

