## **8.5 METHOD OF ASSIGNING PATIENTS TO TREATMENT GROUP**

This is a single-arm treatment study whereby patients who comply with all inclusion/exclusion eligibility criteria will be enrolled. Investigator sites will access an interactive response system to confirm patient enrollment.

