CL:	total body clearance
C _{max} :	maximum plasma concentration
CRS:	cytokine release syndrome
CSR:	clinical study report
CV:	coefficient of variation
DBP:	diastolic blood pressure
DBS:	dried blood spots
DL _{CO} :	diffusing capacity of the lung for carbon monoxide
DP-3:	Developmental Profile 3
ECG:	electrocardiogram
ECHO:	echocardiogram
e-CRF:	electronic case report form
FEV ₁ :	forced expiratory volume in the 1 st second of the FVC maneuver
FVC:	forced vital capacity
Hb:	hemoglobin
HDL:	high density lipoprotein
HIV:	human immunodeficiency virus
HR:	heart rate
HRCT:	high resolution computed tomography
hsCRP:	high sensitivity C-reactive protein
IAR:	infusion-associated reaction

IgE:	immunoglobulin E
IgG:	immunoglobulin G
IL:	interleukin
INR:	international normalized ratio
ITT:	Intent-to treat
IV:	intravenous
LDL:	low density lipoprotein
LLOQ:	Lower Limit of Quantification
MedDRA:	Medical Dictionary for Regulatory Activities
mITT:	Modified intent-to-treat
MN:	multiples of normal
MRI:	magnetic resonance imaging
PCSA:	potentially clinically significant abnormality
PD:	pharmacodynamic(s)
PedsQL:	Pediatric Quality of Life
PFT:	pulmonary function testing
PK:	pharmacokinetic(s)
PKDM:	pharmacokinetics, dynamics and metabolism
Protime:	prothrombin time
PT:	preferred term
PTT:	partial thromboplastin time
QOL:	Quality of Life
QTc:	corrected QT-interval
QTcB:	QTc interval corrected by Bazett
QTcF:	QTc interval corrected by Fridericia
RBC:	red blood cell
rhASM:	recombinant human acid sphingomyelinase
SAE:	serious adverse event
SAP:	Statistical Analysis Plan
SAS:	Statistical Analysis System
SBP:	systolic blood pressure
SD:	standard deviation
SEM:	standard error of the mean
SI:	international system of units, international system of units
SMPD1:	acid sphingomyelinase gene, acid sphingomyelinase gene
SOC:	system organ class
$t_{1/2z}$:	terminal half-life
TEAE:	treatment-emergent adverse event
TLC:	total lung capacity
t_{max} :	time to reach Cmax, time to reach Cmax
ULN:	upper limit of normal
VAS:	visual analogue scale
VLDL:	very low density lipoprotein
V_{ss} :	volume of distribution at steady state.
WBC:	white blood cell
WHO:	World Health Organization

WHO-DRUG: World Health Organization Drug dictionary
WMW: Wilcoxon-Mann-Whitney
 β -HCG: beta-human chorionic gonadotropin

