1.6 STATISTICAL MODIFICATIONS MADE IN THE STATISTICAL ANALYSIS PLAN

The main modifications made in this version of SAP compared to the previously approved version (Version 2, Dated 17-Aug-2016) are listed as follows.

- The modified intent-to-treat population was added in [Section 2.2.2](#) to be consistent with the protocol.
- The per protocol population and completer population were removed from [Section 2.2](#) as they are not pre-defined in the protocol and also are not needed for this study.

- Derivations for classifications of the different SMPD1, CHIT1 and UGT1A1 genotypes were added in [Section 2.3.1](#) in order to provide summaries on number of patients and percentages.
- Protocol-defined potential dose limiting toxicities that are considered AESIs have been added in [Section 2.6.1.3](#) to be consistent with the protocol.
- Specific analyses on infections and bleeding have been updated in [Section 2.6.1.4](#) following interactions with health authorities.
- [REDACTED]
- [REDACTED]
- The paired t-test has been updated to analysis of covariance with baseline included as covariate for exploratory efficacy variables in order to adjust for baseline, since baseline is highly correlated with change from baseline values. See [Section 2.8](#).
- Platelet count and hemoglobin were added as exploratory efficacy endpoints in order to be consistent with other ASMD studies for compound GZ402665/olipudase alfa. See [Section 2.8.4](#).

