2 STATISTICAL AND ANALYTICAL PROCEDURE

Data collected in this study will be presented using summary tables, figures, and by-patient data listings. Descriptive statistics for categorical variables will be provided using frequencies (n) and percentages (%). Descriptive statistics for continuous variables will be provided using number of observations (n), mean, standard deviation (SD), median, minimum, and maximum.

If appropriate, p-values and 95% confidence intervals (CI) from analysis of covariance with baseline as covariate may be provided for change from baseline values. All data used in tabular summaries or figures will be supported by listings of underlying data – raw and/or derived, and all figures will be supported by relevant summary information.

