Percent predicted Hemoglobin-adjusted DLco is calculated as follows:

Percent predicted Hemoglobin-adjusted DLco = 100 * Adjusted DLco / Predicted DLco in unit of mL CO/min/mmHg.

For all 4 tests, FVC (L), FEV₁ (L), TLC (L) and DL_{CO} (mL/min), percent (%) predicted values will be summarized for observed values, change from baseline and percent change from baseline using the mITT population by age group cohorts and overall at scheduled study visit. The analysis of covariance (ANCOVA) with baseline as covariate and WMW test p-values for the change from baseline and percent change from baseline will be provided in the summary tables for all 4 tests. Box plots of observed values over time for these 4 tests will be provided for the mITT population. By-patient plots for all 4 tests over time will be provided.

Additional sensitivity analyses to assess the effect of age group cohorts: ANCOVA will be used for the mITT population for the 4 tests with the following model:

Percent change from baseline at Week 26 or 52 = Age group cohorts + Baseline value.

The summary of percent predicted DLco adjusted for hemoglobin over time will be provided to exclude patients who satisfy the noncompliance condition in [Section 2.1.2](#) as a sensitivity analysis if applicable. In addition, sensitivity analysis to account for missing data of percent predicted DLco adjusted for hemoglobin at baseline or post-baseline visits may be conducted after appropriate imputations.

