2.8.4 Platelet count and hemoglobin

Observed values, change from baseline and percent change from baseline for platelet count and hemoglobin at pre-infusion time point will be summarized by age group cohorts and overall. The ANCOVA with baseline as covariate will be used to assess the change from baseline. Additionally, the ANCOVA with age group cohorts and baseline value as covariates will be used to assess the age effect.

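### SAP 2.8.1 and 2.8.3 name the Wilcoxon-Mann-Whitney test, which needs two independent samples, for within-patient change in a single-arm trial (minor)

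*SAP*

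**What the plan says.** SAP 2.8.1 plans two p-values for spleen and liver volume in multiples of normal. One comes from ANCOVA with baseline as covariate. The other is a rank test: "Wilcoxon-Mann-Whitney (WMW) test p-values for the change from baseline and percent change from baseline will be provided in the summary tables". SAP 2.8.3 repeats the pair for FVC, FEV1, TLC and DLco, with ANCOVA "with baseline as covariate and WMW test p-values for the change from baseline and percent change from baseline will be provided". The list of abbreviations gives "WMW: Wilcoxon-Mann-Whitney". In both sections the tables are by age cohort and overall.

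Protocol 8.5 states: "This is a single-arm treatment study". Protocol 6.4 adds that there is no comparator group. Neither document mentions a signed-rank or one-sample rank test.

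On the ANCOVA, SAP 1.6 records that "The paired t-test has been updated to analysis of covariance with baseline included as covariate for exploratory efficacy variables". SAP 2 says that "p-values and 95% confidence intervals (CI) from analysis of covariance with baseline as covariate may be provided for change from baseline values", SAP 2.8 describes summaries "including the p-value from analysis of covariance with baseline as covariate and 95% CIs as appropriate", and SAP 2.8.4 says that "ANCOVA with baseline as covariate will be used to assess the change from baseline".

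**The concern.** Wilcoxon-Mann-Whitney asks whether values in one independent group tend to be larger than values in another. A change from baseline is one value per patient. In the overall column, or within one cohort, all those values belong to a single group, so the test has nothing to compare them with. The question in these tables is whether patients changed, which calls for a paired or one-sample rank test.

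SAP 1 says that its purpose is to fix the methods before database lock. As written, the programmer must either choose another test after the plan is final or force the named one by treating baseline and post-visit values from the same patients as independent. The second route discards the pairing and can hide a real change.

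**Working it through.** The plan gives no power, alpha or SD for these analyses (SAP 1.3 says that no power calculation was done), so there is no planned figure to reproduce. The check has four steps.

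**1. Is there a second sample in the text?**
- Treatment arms: one (Protocol 8.5), no comparator (Protocol 6.4).
- Age cohorts: three, whereas the test takes two samples. The age effect also has its own ANCOVA in 2.8.1 and 2.8.3.
- Severe versus not severe baseline spleen volume (2.8.1): planned as a summary only, and it would not explain the use in 2.8.3.
- Manufacturing scale: Protocol 11.4.5 plans efficacy by scale, but no visible SAP sentence links it to this test.

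**2. How many p-values are involved?** In the overall column, 2 organs × 2 measures (change, percent change) × 2 visits (Weeks 26 and 52) = 8 in 2.8.1, and 4 tests × 2 × 2 = 16 in 2.8.3. The total is 24.

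**3. What happens if the test is forced on baseline versus post-visit values?** Inputs from the documents: n=20 (the minimum enrolment, Protocol 11.1), the 5 MN spleen eligibility limit (Protocol 7.1), and the 25.3% mean spleen fall in the adult Phase 1b study (Protocol 4.1). Assumptions: baseline lognormal with median 15 MN and no value below 5 MN, CV 0.3 or 0.5; percent change normal with SD 15% and independent of baseline; two-sided 5% level.

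A rough calculation shows the mechanism. At CV 0.3 the baseline SD is about 0.3 × 15 = 4.5 MN, so the standard error of an unpaired difference is about √(2 × 4.5² / 20) = 1.42 MN. The SD of the change is about 0.15 × 15 = 2.25 MN, so the paired standard error is about 2.25 / √20 = 0.50 MN. A 15% fall is 2.25 MN, which is 1.6 unpaired but 4.5 paired standard errors.

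Simulated rejection rates:

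| True mean change | Forced Mann-Whitney, CV 0.3 | Forced Mann-Whitney, CV 0.5 | Signed-rank |
|---|---|---|---|
| 0 | about 0% | about 0% | about 5% |
| −15% | 31% | 3% | 98–99% |
| −25.3% | 97% | 56% | 100% |

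A separate run with percent-change SD 10 or 20 points gave the same pattern. At a 10% fall the forced test rejected 0 to 7% and signed-rank 51 to 98%. At 25.3% the figures were 43 to 98% and about 100%. At no change signed-rank rejected 4.6 to 5.6%.

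**4. Where can signed-rank be informative?** Its smallest two-sided exact p-value is 2/2ⁿ: 0.25 at n=3, 0.125 at n=4, 0.0625 at n=5 and 0.016 at n=7. The cohort minima in Protocol 11.1 are 3 adolescents, 3 + 4 = 7 children and 2 + 2 = 4 infants or young children. At those minima only the child cohort could reach 0.05.

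**The case against.** The strongest reply is that this is loose naming. The sentences speak of change from baseline, so a statistician would probably infer the signed-rank test. ANCOVA p-values stand in the same tables, and the observed values, changes and plots are untouched. All of that stands, and it is why the point is minor. The abbreviation list adds little, because it only expands a term used in the text.

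A second reply is that parts of the SAP are redacted, including two entries in 1.6 and a grouping term in 2.7.2, and that the protocol plans efficacy by manufacturing scale. A two-group use cannot be fully excluded. However, the sentences in 2.8.1 and 2.8.3 are not redacted, and they attach the p-value to change from baseline. The remaining doubt is met by letting the sponsor name the two groups.

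Three stronger readings are tempting, and the documents do not support them:
- **That the p-values cannot be produced at all.** They can be forced, as above. The accurate statement is that the test lacks a stated second sample and performs poorly when forced.
- **That the one-group ANCOVA is also wrong, because the p-value might belong to the uncentred intercept (change at a baseline of zero).** SAP 1.6 presents ANCOVA as the successor to the paired t-test, and SAP 2 and 2.8.4 tie it to change from baseline. This points to the adjusted mean change. The term is not named, so a clarifying sentence would help, but this is not an error.
- **That the age-cohort models leave the tested effect open.** SAP 2.8.1 and 2.8.3 introduce them as assessing the cohort effect, and 2.8.4 as assessing the age effect.

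**Conclusion.** The concern holds for the rank test. Two SAP sections name a two-sample test for within-patient change in a single-arm trial, and no visible text supplies the second sample. This conclusion rests on the documents alone.

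The size of the harm if the test is forced rests on assumed variability and shows direction and order of magnitude only. The error is towards missing a change: the forced test almost never rejects when nothing has changed. No simulation of forcing the test on the pulmonary measures is offered here.

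Severity is minor. The primary objective is safety, efficacy is exploratory, the sample size was not powered, and no decision rule depends on these p-values. The effect is limited to the rank-test p-values: 24 in the overall column, plus the cohort columns if they carry them.

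**What to change.** 1. In SAP 2.8.1 and 2.8.3, replace the Wilcoxon-Mann-Whitney test with the Wilcoxon signed-rank test on within-patient change and percent change from baseline, and update the abbreviation list. If a between-group comparison was intended, for example by manufacturing scale, name the two groups instead.
2. Note that signed-rank p-values cannot fall below 0.05 in cohorts of 3 to 5 patients, so they are informative mainly in the overall column.
3. Optional clarification: state in SAP 2 and 2.8 that the one-group ANCOVA p-value and 95% CI are for the adjusted mean change at the mean baseline of the patients in that model.

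The age-cohort models need no change. A one-sample t interval beside the ANCOVA interval is not needed either, since it would partly restore the method that SAP 1.6 chose to replace.

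The cost is a few words in the SAP and a standard procedure in the software. No new data are needed.

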2.8.2 Height z-score

As stated in [Section 2.6.4](#), patient height will be collected at screening and within 24 hours prior to every infusion visit from Day 1/Week 0 to Week 64 (or withdrawal if withdrawn prematurely). Z-score for height will be evaluated as an exploratory efficacy parameter. This parameter reflects failure to thrive.

Height z-score will be calculated and categorized using the number and percentage of patients in <= -4, > -4 to <= -3.5, > -3.5 to <= -3, > -3 to <= -2.5, > -2.5 to <= -2, > -2 to <= -1.5, > -1.5 to <= -1 and > -1. The categories will be summarized for baseline, Week 12, Week 26, Week 38 and Week 52 by age group cohorts and overall. Change from baseline at Week 52 (as improved, same, and worsened) will also be summarized using the number and percentage of patients. A bar chart for the percentage of patients in each category at baseline and Week 52 will be provided. By-patient plot on height z-score over time will be provided.

Observed values and change from baseline values for height z-score will be summarized at baseline, Week 12, Week 26, Week 38 and Week 52 by age group cohorts and overall. In addition, change from baseline in height z-score will be analyzed with analysis of covariance (ANCOVA) model with baseline height z-score as covariate.

2.8.3 Pulmonary function testing

Pulmonary function testing (PFT) will be performed at Screening, Week 26 and Week 52 (or at withdrawal if withdrawn prematurely and not done within 12 weeks prior to withdrawal) in patients ≥ 5 years old at Day 1/Week 0. PFT will include, but may not be limited to the assessment of forced vital capacity (FVC), forced expiratory volume in the 1st second of the FVC maneuver (FEV₁), total lung capacity (TLC), and diffusing capacity of carbon monoxide (DL_{CO}). Completion of the assessment may depend upon patient cooperation. The tests are done

in local labs and hence do not use a standardized approach for calculation of percent predicted values. For analyses, we use the following standard formula (height and hemoglobin values are from available ones closest to the PFT evaluation date/time, age is calculated at the PFT evaluation date, and sex=0 for female and 1 for male) to calculate the percent predicted values. The percent predicted values captured in the e-CRF will remain in the database, but will not be used for analysis.

Percent predicted values of FEV1 and FVC will use the Global Lung Initiative (GLI) 2012 reference equations (1).

Predicted TLC (Liters) will use the following formula (Koopman et al. corrected version [2]):

$$\text{Predicted TLC} = \exp(24.67 - 4.91 \cdot \ln(\text{Height[cm]}) - 7.16 \cdot \ln(\text{Age[months]}) + 0.059 \cdot \text{Sex} + 1.47 \cdot \ln[\text{Height}] \cdot \ln[\text{Age}])$$

$$\text{Percent predicted TLC} = 100 \cdot \text{Observed TLC} / \text{Predicted TLC}$$

Predicted DLco will be calculated in the unit of mmol/min/kPa as follows (Koopman et al. corrected version [2]):

$$\text{Predicted DLco (mmol/min/kPa)} = \exp(34.80 - 6.89 \cdot \ln(\text{Height[cm]}) - 8.66 \cdot \ln(\text{Age[months]}) + 0.10 \cdot \text{Sex} + 1.79 \cdot \ln[\text{Height}] \cdot \ln[\text{Age}])$$

Unit conversion (Macintyre et al. [3]): mL CO/min/mmHg = mmol/min/kPa * 2.987

Hemoglobin-adjustment factor (Macintyre et al. [3]) (to be applied to DLco in unit of mL CO/min/mmHg)

$$= 1.7 \cdot \text{Hemoglobin (g/dL)} / (10.22 + \text{Hemoglobin}) \text{ for patients } \geq 15 \text{ years of age.}$$

$$= 1.7 \cdot \text{Hemoglobin (g/dL)} / (9.38 + \text{Hemoglobin}) \text{ for patients } < 15 \text{ years of age.}$$

Patients' age at screening will be used to decide which formula to use for the hemoglobin-adjusted factor.

Adjusted DLco = Observed DLco (mL CO/min/mmHg) / Hemoglobin-adjusted factor

Percent predicted Hemoglobin-adjusted DLco is calculated as follows:

Percent predicted Hemoglobin-adjusted DLco = 100 * Adjusted DLco / Predicted DLco in unit of mL CO/min/mmHg.

For all 4 tests, FVC (L), FEV₁ (L), TLC (L) and DL_{CO} (mL/min), percent (%) predicted values will be summarized for observed values, change from baseline and percent change from baseline using the mITT population by age group cohorts and overall at scheduled study visit. The analysis of covariance (ANCOVA) with baseline as covariate and WMW test p-values for the change from baseline and percent change from baseline will be provided in the summary tables for all 4 tests. Box plots of observed values over time for these 4 tests will be provided for the mITT population. By-patient plots for all 4 tests over time will be provided.

Additional sensitivity analyses to assess the effect of age group cohorts: ANCOVA will be used for the mITT population for the 4 tests with the following model:

Percent change from baseline at Week 26 or 52 = Age group cohorts + Baseline value.

The summary of percent predicted DLco adjusted for hemoglobin over time will be provided to exclude patients who satisfy the noncompliance condition in [Section 2.1.2](#) as a sensitivity analysis if applicable. In addition, sensitivity analysis to account for missing data of percent predicted DLco adjusted for hemoglobin at baseline or post-baseline visits may be conducted after appropriate imputations.

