6 APPENDICES

Adjustment of DLco measurements

1 Introduction

Adjustments of DLco measurements are described in detail the 2005 ERS/ATS statement. In the paper, however, the adjustment is described as a change of the DLco predicted values. After several discussions with opinion leaders, we have to conclude that it is more common to compute a DLadj value that is computed from the measured DLco value. This DLadj value is then compared to the (unchanged) predicted values. The following table describes this:

Comment	Parameter	Predicted	% Predicted
	DLcomeas	DLcopred	DLcopred/DLcomeas
ERS/ATS statement	DLcomeas	DLcopred $^*\alpha$	DLcopred $^*\alpha$ /DLcomeas
EasyOne pro	DLadj = DLcomeas $^*\beta$	DLcopred	DLcopred/(DLcomeas $^*\beta$)

As can be seen from the table above, the % Predicted is the same if $\beta = 1/\alpha$. This means that the equations of the ERS/ATS statement have to be inverted (ie, the factor is multiplied instead of divided). If compared to the original formulas in the ERS/ATS statement, the following formulas are therefore 'inverted' (multiplication instead of division and vice versa).

2 Adjustment for hemoglobin

The following formula is applied to correct for hemoglobin (Hb):

Male adults (age ≥ 15): $DLadj = DLco / (1.7 * Hb / (10.22 + Hb))$ Hb in g/dL

Female and children (age < 15): $DLadj = DLco / (1.7 * Hb / (9.38 + Hb))$ Hb in g/dL

Unit conversion: $Hb [g/dL] = Hb [mmol/L] / 0.616$

(according to other sources the factor is 0.6206)

Allowed range for Hb: 0 to 100 g/dL

Default value for male adults (age ≥ 15): 14.6 g/dL (9.00 mmol/L)

Default value for female and children (age < 15): 13.4 g/dL (8.26 mmol/L)

Signature Page for VV-CLIN-0195653 v3.0

dfi13803-16-1-9-sap

Approve & eSign

[REDACTED]
[REDACTED]
Clinical

Approve & eSign

[REDACTED]
[REDACTED]

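### SAP 2.8.3 picks the hemoglobin correction for DLco by age alone, so girls aged 15 or over get the formula the SAP's appendix reserves for males, and their adjusted DLco is about 4% too high

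*SAP*

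**What the plan says.** SAP 2.8.3 (Pulmonary function testing) defines a hemoglobin factor of 1.7 × Hb / (10.22 + Hb) for patients aged 15 or over and 1.7 × Hb / (9.38 + Hb) for patients under 15, with Hb in g/dL. Only age selects between them: "age at screening will be used to decide which formula to use for the hemoglobin-adjusted factor". The factor is then a divisor: "Adjusted DLco = Observed DLco (mL CO/min/mmHg) / Hemoglobin-adjusted factor". The analysed variable follows from it: "Percent predicted Hemoglobin-adjusted DLco = 100 * Adjusted DLco / Predicted DLco", both in mL CO/min/mmHg. Sex is coded in the same section, but it enters only the predicted TLC and predicted DLco equations.

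The SAP appendix on adjustment of DLco measurements gives the same two formulas but allocates them differently. The 10.22 version is for adult males, defined as aged 15 or over. The 9.38 version is for females and for children under 15. The default hemoglobin values are split the same way: 14.6 g/dL for males aged 15 or over, and for everyone else "Default value for female and children (age < 15): 13.4 g/dL".

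Neither SAP 1.5 nor the visible text of SAP 1.6 mentions a decision to drop sex from the rule. Two items in 1.6 are redacted.

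**The concern.** The adolescent cohort runs from 12 to under 18 years, so girls aged 15 to 17 are eligible, and the two parts of the SAP give them different constants. Two programmers working from different pages would produce different values for the same patient. Because the factor is a divisor, the larger constant gives a smaller factor and a higher adjusted DLco, so the rule in 2.8.3 makes these girls' lung function look better than it would under the appendix.

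The variable has some weight in this SAP. Percent predicted hemoglobin-adjusted DLco is the only pulmonary function measure for which 2.8.3 provides noncompliance and missing-data sensitivity analyses, and SAP 2.3.1 uses it to define a severe baseline category (below 40%). Results are summarized by age cohort, and the planned minimum for the adolescent cohort is 3 patients, so one affected girl could visibly move a cohort mean or a severity count.

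**Working it through.** **Inputs.** Constants 10.22 and 9.38: SAP 2.8.3 and appendix. Default hemoglobin 14.6 and 13.4 g/dL: appendix. Severity cut of 40%: SAP 2.3.1. The documents give no hemoglobin distribution for the trial patients, so 8 to 16 g/dL is assumed as a range.

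**Step 1: do the appendix formulas agree with the appendix defaults?** At its default hemoglobin a formula should leave DLco unchanged.

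- Males aged 15 or over: 1.7 × 14.6 / (10.22 + 14.6) = 24.82 / 24.82 = 1.000
- Females and children: 1.7 × 13.4 / (9.38 + 13.4) = 22.78 / 22.78 = 1.000

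Both do. Under 2.8.3, a girl of 15 with hemoglobin 13.4 g/dL gets 1.7 × 13.4 / (10.22 + 13.4) = 22.78 / 23.62 = 0.964, so her DLco is raised when the appendix says it needs no correction.

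**Step 2: size of the difference.** Observed DLco, predicted DLco and the term 1.7 × Hb are the same under both rules and cancel. The ratio of the 2.8.3 value to the appendix value is

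(10.22 + Hb) / (9.38 + Hb).

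| Hb (g/dL) | Ratio | Overstatement |
|---|---|---|
| 8 | 18.22 / 17.38 = 1.0483 | 4.8% |
| 10 | 20.22 / 19.38 = 1.0433 | 4.3% |
| 12 | 22.22 / 21.38 = 1.0393 | 3.9% |
| 13.4 | 23.62 / 22.78 = 1.0369 | 3.7% |
| 16 | 26.22 / 25.38 = 1.0331 | 3.3% |

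**Step 3: effect on reported levels.** At 12 g/dL, 60% predicted under the appendix rule becomes 60 × 1.0393 = 62.4%. The value that 2.8.3 would report as exactly 40% is 40 / 1.0393 = 38.5%, so a baseline from about 38.5% to just under 40% leaves the severe class. That lower edge moves with hemoglobin: 38.3% at 10 g/dL and 38.6% at 13.4 g/dL.

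**Step 4: effect on change from baseline.** Age at screening fixes the constant for every visit, so the bias largely cancels in a ratio. If hemoglobin rises from 10 to 13 g/dL, the follow-up/baseline ratio is multiplied by 1.0375 / 1.0433 = 0.994, a shift of about −0.6%. As an illustration, take 50% rising to 65% predicted under the appendix rule:

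- Percent change is +30.0% under the appendix rule and +29.3% under 2.8.3.
- Absolute change is 15.0 points under the appendix rule and 65 × 1.0375 − 50 × 1.0433 = 15.3 points under 2.8.3. If hemoglobin moves only from 12 to 12.5 g/dL, it is 15.5 points.

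**The case against.** The strongest reply is that 2.8.3 is the operative analysis text, cites a published standard for its factor, and does not refer to the appendix. The appendix names a device and describes itself as a restatement of that kind of standard. On this view the documents prove a contradiction, not which side is right. Part of this stands: the words overstated and inflated hold relative to the appendix. But the appendix says it describes the 2005 ERS/ATS statement, which matches the 2005 standardisation document on carbon monoxide uptake that 2.8.3 cites. Its constants also fit its own sex-specific defaults, and 2.8.3 gives no reason for leaving sex out. The appendix label for females and children could be read as limiting females to those under 15, but girls of 15 or over would then have no formula at all. On either reading 10.22 is restricted to males.

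The other objections limit the impact and are fair:

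- All of the additional patients are under 12. With exactly 12 staggered patients and the stated minimums of 3 children and 2 infants, adolescents number between 3 and 12 − 3 − 2 = 7, so affected girls may be very few or none.
- The endpoint is exploratory, in a single-arm study whose primary objective is safety.
- Percent change is almost untouched and, when hemoglobin rises, moves slightly against the patient.
- The severe DLco class is a baseline descriptor. Unlike spleen severity, it defines no planned outcome subgroup.
- The sensitivity analyses are conditional or optional.

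**Conclusion.** The concern holds. SAP 2.8.3 contradicts the SAP's appendix for girls aged 15 to under 18 at screening, and the documents support the appendix's allocation. Taking the appendix as the reference, 2.8.3 overstates their adjusted DLco and percent predicted value by 3.6% to 4.3% over hemoglobin 10 to 14 g/dL, and by 3.3% to 4.8% over the wider assumed range of 8 to 16 g/dL. The effect is on observed levels, the baseline and possibly the below-40% class. Percent change is affected by well under one percentage point in the example worked. Boys and all patients under 15 are unaffected. No main conclusion of the study depends on this, but it should be corrected because the rule is wrong as written and the correction costs almost nothing.

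A separate clerical slip is in the appendix table, whose percent-predicted column is upside down ("DLcopred/DLcomeas"). Section 2.8.3 states the ratio the right way round, so no analysis changes.

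**What to change.** In SAP 2.8.3, select the factor by sex as well as age at screening: 1.7 × Hb / (10.22 + Hb) for males aged 15 or over, and 1.7 × Hb / (9.38 + Hb) for females of any age and for males under 15. If the age-only rule was intended, say so, justify it, and align the appendix. In the same edit, turn the appendix percent-predicted cells into measured (or adjusted) over predicted.

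The cost is a few words of SAP text and one added condition in the derivation. Sex is already in the data and in the predicted DLco equation, so nothing new has to be collected.
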